5.6 Protocol Deviations

The date of and reason for protocol deviations will be documented in all cases.

Protocol assessments will continue until the end of the study, unless the protocol deviations put the subject at risk or the subject's condition requires that he/she be discontinued from the study.

6.0 ADVERSE EVENTS³⁴

6.1 Definition of Adverse Events

Information about every adverse event (AE) will be collected and recorded.

- Any untoward medical occurrence, unintended disease or injury or any untoward clinical signs (including an abnormal laboratory finding) in subjects, users or other persons whether or not related to the investigational medical device.

NOTE 1: This definition includes events related to the investigational device or the comparator.

NOTE 2: This definition includes events related to the procedures involved.

NOTE 3: For users or other persons, this definition is restricted to events related to investigational medical devices.

A treatment-emergent AE (TEAE) is defined as an AE that meets either of the following conditions:

- Begins on or after the first instillation of investigational medical device on Visit 2 (Day 0).
- Begins before Visit 2 (Day 0), and worsens in severity on or after the first instillation of investigational medical device on Visit 2 (Day 0).

6.2 Definition of Adverse Device Effect

Information about every adverse device effect (ADE) will be collected and recorded.

Adverse event related to the use of an investigational medical device.

NOTE 1- This includes any adverse event resulting from insufficiencies or inadequacies in the instructions for use, the deployment, the implantation, the installation, the operation, or any malfunction of the investigational medical device.

NOTE 2- This includes any event that is a result of a use error or intentional abnormal use of the investigational medical device.

The Investigator is obliged to determine the severity of the event and evaluate the causal relationship of the event to the investigational medical device.

6.3 Definition of Serious Adverse Events

Information about every serious adverse event (SAE) will be collected and recorded.

Adverse event that:

- led to a death, injury or permanent impairment to a body structure or a body function
- led to a serious deterioration in health of the subject, that either resulted in:
 - a life-threatening illness or injury, or
 - a permanent impairment of a body structure or a body function (e.g., blindness), or
 - in-patient hospitalization or prolongation of existing hospitalization, or
 - medical or surgical intervention to prevent life threatening illness
- Led to foetal distress, foetal death or congenital abnormality or birth defect.

NOTE 1: Planned hospitalization for pre-existing condition, or a procedure required by the Clinical Investigation Plan, without a serious deterioration in health, is not considered a serious adverse event.

A medically significant event that does not result in any of the above, may be considered an SAE when, based upon appropriate medical judgment, the event may jeopardize a subject condition and may require medical or surgical intervention to prevent one of the outcomes listed in this definition.

6.4 Definition of Serious Adverse Device Effect

Information about every serious adverse device effect (SADE) will be collected and recorded.

Adverse device effect that has resulted in any of the consequences characteristic of a serious adverse event.

6.5 Definition of Unanticipated Serious Adverse Device Effect and Anticipated Serious Adverse Device Effect

Information about every Unanticipated Serious Adverse Device Effect and Anticipated Serious Adverse Device Effect (ASADE) will be collected and recorded.

Serious adverse device effect which by its nature, incidence, severity or outcome has not been identified in the current version of the risk analysis report is considered as an unanticipated serious adverse device effect (USADE).

An anticipated serious adverse device effect (ASADE) is an effect which by its nature, incidence, severity or outcome has been identified in the risk analysis report.

6.6 Definition of Device Deficiency (DD)

Information about Device Deficiency (DD) will be collected and recorded.

Inadequacy of an investigational medical device related to its identity, quality, durability, reliability, safety or performance. This may include malfunctions, use error, or inadequacy in the information supplied by the manufacturer.

Device Deficiency that might have led to a SAE if:

- a) suitable action had not been taken or
- b) intervention had not been made or
- c) circumstances had been less fortunate

6.7 Causality assessment

The relationship between the use of the investigational medical device (including the procedure) and the occurrence of each adverse event shall be assessed and categorized as follows:

1) Not related: relationship to the device or procedures can be excluded when:

- the event is not a known side effect of the product category the device belongs to or of similar devices and procedures;
- the event has no temporal relationship with the use of the investigational device or the procedures;
- the event does not follow a known response pattern to the medical device (if the response pattern is previously known) and is biologically implausible;
- the discontinuation of medical device application or the reduction of the level of activation/exposure - when clinically feasible - and reintroduction of its use (or increase of the level of activation/exposure), do not impact on the event;
- the event involves a body-site or an organ not expected to be affected by the device or procedure;
- the event can be attributed to another cause (e.g. an underlying or concurrent illness/ clinical condition, an effect of another device, drug, treatment or other risk factors);
- harms to the subject are not clearly due to use error.

In order to establish the non-relatedness, not all the criteria listed above might be met at the same time, depending on the type of device/procedures and the event.

2) Unlikely: the relationship with the use of the device seems not relevant and/or the event can be reasonably explained by another cause, but additional information may be obtained.

3) Possible: the relationship with the use of the investigational device is weak but cannot be ruled out completely. Alternative causes are also possible (e.g. an underlying or concurrent illness/ clinical condition or/and an effect of another device, drug or treatment). Cases where relatedness cannot be assessed or no information has been obtained should also be classified as possible.

4) Probable: the relationship with the use of the investigational device seems relevant and/or the event cannot reasonably be explained by another cause, but additional information may be obtained.

5) Causal relationship (Certain): the event is associated with the investigational device or with procedures beyond reasonable doubt when:

Study #CBL-2017-01- Protocol

- the event is a known side effect of the product category the device belongs to or of similar devices and procedures;
- the event has a temporal relationship with investigational device use/application or procedures;
- the event involves a body-site or organ that
 - . the investigational device or procedures are applied to;
 - . the investigational device or procedures have an effect on;
- the event follows a known response pattern to the medical device (if the response pattern is previously known);
- the discontinuation of medical device application (or reduction of the level of activation/exposure) and reintroduction of its use (or increase of the level of activation/exposure), impact on the event (when clinically feasible);
- other possible causes (e.g. an underlying or concurrent illness/ clinical condition or/and an effect of another device, drug or treatment) have been adequately ruled out;
- harm to the subject is due to error in use.

In order to establish the relatedness, not all the criteria listed above might be met at the same time, depending on the type of device/procedures and the event.

Related adverse events (including serious adverse events) are AEs with at least a possible relationship to the investigational medical device or procedure.

6.8 Reporting Adverse Events and Follow-up

Throughout the course of the study, efforts will be made by the Investigator to remain alert to possible AEs that are either systemic or ocular in nature. The period of observation for collection of AEs extends from the time the subject gives informed consent until the last study visit, Visit 5 (Day 90 ± 10 days). The first concern will be the safety of the subject, and appropriate medical intervention will be made.

The Investigator or designee will elicit reports of AEs from the subject at each study visit and record all AEs. An assessment of each event will be made by the Investigator as to severity and causal relationship to investigational medical device, as well as, start and end dates.

The subject will be instructed to contact the Investigator immediately if any unusual systemic or ocular AEs occur between visits.

Additional assessments/visits may be scheduled, as necessary, to ensure the safety of the subject, during the study period. A subject who discontinues due to an AE should be seen for post-study follow-up visits as necessary.

Non-serious AEs that are ongoing at the study exit visit will be followed by the Investigator up to 30 days after the subject exits the study.

6.9 Reporting Serious Adverse Events and Follow-up

Any SAE must be reported to the Sponsor, independent of the circumstance or suspected cause, **within 24 hours** from the time the event was reported to the Investigator.

All SAEs (whether or not considered related) experienced from consent through 30 days from the last dose of the investigational medical device must be reported to the Sponsor regardless of the causal relationship to the investigational medical device. Following Visit 5 (Study Exit, Day 90 ± 10 days) + 30 days or early discontinuation from the study+30 days, only SAEs considered related to the study should be reported within 24 hours to the Sponsor (cf Personnel and Facilities page).

Within 24 hours of notification the Investigator will fax or send by e-mail using contact details provided in Personnel and Facilities page completed Serious Adverse Event Report to the Sponsor contact. For SAEs with fatal outcomes, a summary of available autopsy findings should be submitted within 24 hours from the time the document was reported to the Investigator.

The Sponsor / Sponsor Representative will notify the EC in writing of any SAE in accordance with the EC requirements.

The Sponsor will be responsible for submitting SAE reports to regulatory authorities based on applicable regulations. The Sponsor / Sponsor Representative will also send notifications to all participating Investigators of any SAE that is unanticipated and associated with the study. It is important that the Principal Investigator reviews these expedited reports, as they contain safety information that may be relevant to each of the participating subjects. For related SAEs that resulted in death, life-threatening events, imminent risk of death, or serious injury/illness that requires prompt remedial action, SAEs will be submitted to the applicable regulatory authorities within 2 calendar days from the time the Sponsor becomes aware of the event. All other related SAEs and investigational medical device deficiency that might have led to an SAE will be submitted within 7 calendar days.

If the Investigator becomes aware of any new information regarding an SAE (ie, resolution, change in condition, or new treatment), a new Serious Adverse Event Form must be completed and faxed or e-mailed to the Sponsor using contact details provided in Personnel and Facilities page within 24 hours. The original SAE form is not to be altered. The report should describe whether the event has resolved or continues and how the event was treated.

Serious adverse events that have previously been reported and continue after the subject's discontinuation or completion of the study will be followed until their medical endpoints are determined or until no further change in the conditions is expected. The events and endpoints will be reported in writing by the Investigator to the Sponsor (cf Personnel and Facilities page).

Following the subject's discontinuation or completion of the study, for any timeframe afterward deemed medically significant, any SAEs, which are assessed as causally related to the investigational medical device, should also be reported to the Sponsor (cf Personnel and Facilities page).

6.10 Reporting Pregnancies and Follow-up

In the event that a study subject becomes pregnant, a notification will be sent to the Sponsor (cf Personnel and Facilities page), regardless of whether an AE/SAE was reported. All pregnancies will be followed to term. Every effort will be made to obtain

the health status of the mother and infant or the fetus (in cases of miscarriage or therapeutic abortion).

6.11 Reporting Complaints for Ancillary Marketed Bausch & Lomb Products

For Bausch & Lomb marketed products used as ancillary products in the study, the Investigator should report any complaints, malfunctions, or similar events related to these products as they would in their normal clinical practice.

6.12 Submitting an Expedited Safety Report to Competent Authorities

All SAE must be fully recorded and notified to all competent authorities of member States in which the clinical investigation is being performed within the required timeframe (whether or not the event is unanticipated or anticipated) In addition, any unanticipated SAE related to a subject's participation in the study (or conduct of study), regardless if the investigational product was administered, will be evaluated by Materiovigilance to determine if expedited reporting is required. For example, an unanticipated, serious and severe reaction which could be associated to the study procedures, and which could modify the study conduct requires expedited reporting.

The Sponsor will compile the report and submit the expedited safety report to the EC and competent authority within the required reporting timeframe.

7.0 STATISTICAL METHODS

7.1 Study Endpoints

7.1.1 Primary Performance Endpoints

The primary performance endpoint for this study is mean change from baseline (CFB) in the study eye at Visit 4 (Day 28 ± 3 days) in ocular surface fluorescein staining score, combining corneal, nasal and temporal bulbar conjunctival fluorescein staining, each graded 0 to 5, according to the Oxford Scheme. The investigator will record the total score per eye (the maximum score is 15 [maximum of 5 for each of the 3 areas]).

The study eye will be the eligible eye with the highest total ocular surface fluorescein staining score at baseline or, if both eyes are eligible and have the same score, the study eye will be the right eye.

7.1.2 Secondary Performance Endpoints

The secondary performance endpoints include the following:

- Mean CFB in the study eye at Visit 5 in total ocular surface fluorescein staining score
- Mean CFB in the study eye in fluorescein staining score for each area (cornea, nasal conjunctiva and temporal conjunctiva) at Visits 4 and 5
- Mean CFB in the study eye in TFBUT at Visits 4 and 5
- Evolution from baseline of Ocular Surface Disease-Quality of Life (OSD-QoL[®]) questionnaire scores at Visit 5 for all 7 dimensions: Daily Activities, Handicap

and Work Difficulties, Giving up Make-up, Acknowledgement, Acceptance, Fear for the Future, and Emotional Well-Being.

- Mean CFB in the global sum score of dry eye symptoms at Visits 4 and 5: sensation of dryness, foreign body, burning, stinging, itching, blurred vision, sensitivity to light, each graded from 0 to 4
- Mean CFB in the study eye in volume of tear fluid secretion as assessed by the unanaesthetized Schirmer test at Visit 4
- Frequency of investigational eye drop instillations, as reported in subject diary

7.1.3 Safety Endpoints

The safety endpoints include the following:

- Occurrence rates of ocular and non-ocular TEAEs.
- Visual Acuity measured with habitual correction, using Monoyer chart.

7.1.4 Tolerability and Ease-of-Use Endpoints

The tolerability endpoints are as follows:

- Assessment of investigational eye drop tolerability upon instillation as reported in subject diary
- Assessment of ease-of-use of the bottle as reported in subject diary

7.2 Hypotheses

$H_0: (\mu_{CBL-102 \text{ Eye Drops}} - \mu_{Vismed} \geq 2)$

versus

$H_1: (\mu_{CBL-102 \text{ Eye Drops}} - \mu_{Vismed} < 2)$

Where μ = mean CFB in the study eye at Visit 4 (Day 28 \pm 3 days) in total ocular surface staining score.

7.3 Sample Size

A validated macro SAS v. 9.4 was used for sample size calculation. Assuming a unilateral α risk of 2.5%, a β risk of 10% (90% power), a non-inferiority margin of 2 and a standard deviation of 2.5 on the primary endpoint²², a sample size of 33 evaluable subjects per treatment group is necessary to demonstrate non-inferiority of CBL-102 Eye Drops to Vismed® Multi.

With a projected dropout rate of 10% and a protocol violation rate of 10%, a total of approximately 84 subjects with moderate to severe dry eye will be randomized in this clinical investigation.

7.4 Randomization

A total of 84 subjects will be randomized to receive CBL-102 Eye Drops or Vismed® Multi in a 1:1 ratio.

7.5 Analysis Sets

The analysis sets that will be used in this study are:

- Intent-to-Treat (ITT) Population:** includes all subjects who were randomized, who received at least 1 eye drop instillation and have a baseline and at least 1 post-baseline assessment. The ITT population will be used to analyze all performance endpoints. Subjects will be analyzed according to the treatment to which they were randomized. It is expected that subjects will be dispensed a correct investigational medical device. However, if a subject does receive incorrect investigational medical device, the impact to the study results will be investigated using ad hoc analyses.
- Per Protocol (PP) Population:** includes all of the subjects in the ITT population who remained in the study through Visit 4 (Day 28) and who did not have any major protocol deviations. The PP population will be used for the primary performance analysis and for secondary performance endpoints.
- Safety Population:** includes all subjects who received at least 1 dose of investigational eye drops.

7.6 Statistical Analysis

7.6.1 Methods of Analysis

Summaries for continuous variables will include the sample size (n), mean, standard deviation (SD), median, minimum, and maximum. Calculations will be based on the number of subjects (or eyes) with non-missing values for the study population being summarized.

Summaries for discrete variables will include frequencies and percentages. Percentages will be based on the number of subjects (eyes) with non-missing values. The denominator for percents will be the number of subjects (eyes) from the study population being analyzed. For each subject, baseline will be defined as the last non-missing measure prior to initiation of investigational treatment and endpoint will be defined as the measure of any follow-up scheduled visit. Change from baseline will be defined as (follow-up measure – baseline measure) and will be calculated if both baseline and follow-up endpoint are not missing.

The study eye will be the eligible eye with the highest total ocular surface fluorescein staining score at baseline or, if both eyes are eligible and have the same score, the study eye will be the right eye.

For each subject, the number of investigational eye drops used per day and for how many days during the course of study will be evaluated. It is expected that most subjects will not perform more than 6 applications per day on a continued regularly basis during the study.

The primary performance endpoint (mean change from baseline in total ocular surface fluorescein staining score) will be analyzed using analysis of covariance (ANCOVA) model. The model will include terms of treatment and baseline ocular surface staining score as covariates. Sensitivity analyses including investigator site as covariate will be performed. A 2-sided 95% confidence interval (CI) based on the ANCOVA model will be computed for the effect difference (CBL-102 Eye Drops *minus* Vismed® Multi). Non-

inferiority will be demonstrated if the upper bound of the 95% CI is less than 2 grades in the PP analysis. Supportive analysis of the primary endpoint will be performed on ITT population. The same ANCOVA model used to analyze the primary endpoint will be employed to analyze secondary continuous performance endpoints. Supportive analyses on secondary performance endpoints will be performed in the ITT and PP populations.

Ocular biomicroscopic assessment will be summarized at each visit using discrete summary statistics and presented by treatment.

Treatment-emergent systemic AEs will be summarized using discrete summary statistics at the subject and event level by system organ class and preferred term for each treatment group. Treatment-emergent ocular AEs will be summarized for treated eyes and fellow eyes separately. Similarly, TEAEs will be summarized by severity and relationship separately.

Categorical endpoints will be analyzed using Fisher's exact test or chi-square test where it is appropriate.

All the statistical tests will be performed at significance level $\alpha=0.05$.

The details of the analysis will be documented in the Statistical Analysis Plan (SAP) which will be reviewed at the masked data review and finalized before breaking the treatment codes.

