Statistical methods:	
A validated macro SAS v. 9.4 was used for sample size calculation. Assuming a unilateral α risk of 2.5%, a β risk of 10% (90% power), a non-inferiority margin of 2 and a standard deviation of 2.5 on the primary endpoint, a sample size of 33 evaluable subjects per treatment group is necessary to demonstrate non-inferiority of CBL-102 Eye Drops to Vismed® Multi.
 
With a projected dropout rate of 10% and a protocol violation rate of 10%, a total of approximately 84 subjects with moderate to severe dry eye will be randomized in this clinical investigation.
 
Summaries for continuous variables will include the sample size, mean, standard deviation (SD), median, minimum, and maximum. Calculations will be based on the number of subjects (or eyes) with non-missing values for the study population being summarized. Summaries for discrete variables will include the tabulation of frequencies and percentages. Percentages will be based on the number of subjects (eyes) with non-missing values. The denominator for percentage will be the number of subjects (eyes) from the study population being analyzed.
 
The primary performance endpoint is the mean CFB to Day 28 in total ocular surface fluorescein staining score (corneal, nasal and temporal bulbar conjunctival fluorescein staining) with each area graded (0 to 5) according to the Oxford Scheme. The investigator will record the total score per eye (the maximum score is 15).
 
The study eye will be the eligible eye with the highest total ocular surface staining score at baseline or, if both eyes are eligible and have the same score, the study eye will be the right eye. An analysis of covariance (ANCOVA) model with main effects of treatment and baseline ocular surface staining score as covariates will be used to analyze the primary endpoint. Sensitivity analyses including investigator site as covariate will be performed. A 95% 2-sided confidence interval (CI) based on the ANCOVA model will be computed for the effect difference (CBL-102 Eye Drops minus Vismed® Multi). Non-inferiority will be demonstrated if the upper bound of the 95% CI is less than 2 grades in the per protocol (PP) analysis. Supportive analysis of the primary endpoint will be performed on the intent-to-treat (ITT) population. The same ANCOVA model will be used to analyze secondary continuous endpoints. Supportive analyses on secondary performance endpoints will be performed in the ITT and PP populations. Safety endpoints analysis will be performed on the safety population.

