2.2.3 Subject Discontinuation

A subject MAY be discontinued (at the discretion of the Investigator, the Sponsor, and/or the EC) prior to the final visit for several reasons, including, but not limited to:

- A serious adverse event (SAE) occurring during the course of the study, which precludes continued treatment or follow-up
- The subject not following required study procedures
- If a subject exhibits intolerable AEs (related or not related to the investigational medical device), or if a subject fails to show improvement or the clinical status worsens, the treating Investigator may opt to withdraw the subject from the study and implement necessary intervention.

A subject MUST be discontinued prior to the final visit for any of the following reasons:

- Voluntary withdrawal
- Death
- Investigator decision that it is not in the best medical interest of the subject to continue participation in the investigation. In case a subject administers more than 8 instillations per day for both eyes on a regularly continued basis (approximately 70 %) as assessed on Visit 4, the subject will be discontinued from the study and the investigator will prescribe an appropriate treatment.

Prior to discontinuing a subject, every effort should be made to contact the subject, schedule a final visit, obtain as much follow-up data as possible, and to retrieve all investigational materials. Adverse events will be followed as described in Section 6.5 . Subject withdrawals will be documented clearly on the source document and applicable electronic case report form (eCRF). The assessments scheduled for Visit 5 should be performed at this early termination visit.

Notification of subject discontinuation will be made to the Sponsor Representative and will be clearly documented on the applicable eCRF. Any subject discontinued from the study will not be replaced.

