7.6.9 Missing Data

For subjects who discontinue the study early, analyses of change from baseline to endpoint for continuous variables will be based on the last non-missing post-baseline data (last observation carried forward data imputation methodology).

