APPENDIX A: SCHEDULE OF VISITS AND PARAMETERS

All study tasks should be performed by qualified study site personnel as indicated on the delegation of authority log under the supervision of the Principal Investigator. Furthermore, all ocular signs must be evaluated by an ophthalmologist.

PROCEDURE/ASSESSMENTS	Visit 1	Visit 2	Visit 3	Visit 4	Visit 5
	Screening	Inclusion	Follow-up Telephone call ^d	Follow-up	Study Exit
	ART run in	Baseline			
	Day -14 (up to -16 days)	Day 0	Day 7 (± 1 day)	Day 28 (± 3 days)	Day 90 (± 10 days)
Informed Consent	X				
Demographic data	X				
Current and relevant medical and ocular history	X				
Pregnancy test, if applicable	X				
Concomitant medication	X	X	X	X	X
Dry eye symptoms	X	X		X	X
OSD-QoL® questionnaire		X			X
Visual acuity	X	X	X ^e	X	X
Biomicroscopy	X	X	X ^e	X	X
TFBUT	X	X		X	X
Fluorescein staining	X	X		X	X
Schirmer test		X		X	
Eligibility determination	X	X			
Randomization		X			
Dispense run-in ART	X				

Version 3, 25 Jul 2017

A-1

Study #CBL-2017-01- Protocol

PROCEDURE/ASSESSMENTS	Visit 1	Visit 2	Visit 3	Visit 4	Visit 5
	Screening	Inclusion	Follow-up Telephone call ^d	Follow-up	Study Exit
	ART run in	Baseline			
	Day -14 (up to -16 days)	Day 0	Day 7 (\pm 1 day)	Day 28 (\pm 3 days)	Day 90 (\pm 10 days)
Collect run-in ART		X			
Dispense diary ^a	X	X		X	
Collect diary ^b		X		X	X
Dispense investigational eye drops		X		X	
Collect investigational eye drops in a sealed container					X
Review subject diary for compliance		X	X ^e	X	X
Adverse events ^c	X	X	X	X	X
Exit subject					X

Abbreviations: ART = artificial tears; OSD-QoL = Ocular Surface Disease-Quality of Life; TFBUT = tear film break-up time

^a Diary A will be dispensed at Visit 1, Diary B will be dispensed at Visit 2, and Diary C will be dispensed at Visit 4

^b Diary A will be collected at Visit 2, Diary B will be collected at Visit 4, and Diary C will be collected at Visit 5

^c Adverse events will be collected from the time the subject signs the ICF to study exit

^d Telephone call assessment for compliance and collection of adverse events by the Investigator or designee. The Investigator should determine whether subject should come for a visit or not

^e If visit performed

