## 7.5 Primary performance endpoint analysis

The primary performance endpoint is the mean CFB in the study eye at visit 4 (D28  $\pm$  3 days) in ocular surface fluorescein staining score, combining corneal, nasal and temporal bulbar conjunctival fluorescein staining score, each graded from 0 to 5, according to the Oxford scheme.

The primary performance endpoint analysis will be performed on the per-protocol population.

The primary performance endpoint will be analyzed by an analysis of covariance including the treatment as fixed effect and the baseline ocular surface staining score as covariate (SAS® Mixed procedure). The two-sided 95% confidence interval for the difference [CBL-102 Eye Drops: D28-D0] – [Vismed Multi: D28-D0] will be computed by the model. The non-inferiority will be demonstrated if the upper bound of the 95% CI is less than 2.

In addition to this model, and depending on the results of the baseline characteristics description, other relevant baseline covariates could be added to the model.

A sensitivity analysis including investigator site as covariate will also be performed using the same model. Mean CFB by treatment and by center will be displayed (if necessary, small centers will be grouped).

Summary statistics for continuous variables will be presented for the total ocular surface fluorescein staining score at D0, D28, and for CFB at D28 for each treatment group.

This analysis will also be performed on patients from the ITT population.

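### Non-inferiority is decided on the per-protocol set alone, so early failures that lead to withdrawal before Day 28 carry no weight, and nothing covers PP success with ITT failure

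*Protocol*

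**What the plan says.** **Decision rule.** Protocol 7.6.1 states that non-"inferiority will be demonstrated if the upper bound of the 95% CI is less than 2 grades in the PP analysis". The synopsis (Statistical methods) has the same rule: non-"inferiority will be demonstrated if the upper bound of the 95% CI is less than 2 grades in the per protocol (PP) analysis". SAP 7.5 agrees: "The primary performance endpoint analysis will be performed on the per-protocol population". In all three places the ITT analysis is a supportive or additional run of the same model, with no success criterion attached. SAP section 4, which lists modifications to the protocol's statistics, does not change this.

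**Who is in PP.** Under Protocol 7.5 the set "includes all of the subjects in the ITT population who remained in the study through Visit 4 (Day 28") and had no major deviation. SAP section 5 uses the same definition.

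**Who may leave early.** Protocol 2.2.3 allows withdrawal for intolerable adverse events and adds that "if a subject fails to show improvement or the clinical status worsens, the treating Investigator may opt to withdraw the subject".

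**What is measured when they leave.** Protocol 2.2.3: "The assessments scheduled for Visit 5 should be performed at this early termination visit". Visit 5 includes fluorescein staining. For early discontinuers, Protocol 7.6.9 says that change from baseline "will be based on the last non-missing post-baseline data (last observation carried forward data imputation methodology"); SAP 7.12 repeats this.

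**What is scheduled before Day 28.** Visit 3 is, per Appendix A, a "Telephone call assessment for compliance and collection of adverse events by the Investigator or designee". If the subject is called in, only visual acuity and biomicroscopy are added.

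**The concern.** The PP completion rule can exclude a subject because of outcome. Someone who does badly on the test product and is withdrawn at, say, Day 14 has broken no rule and may have a staining score from the termination visit. That score can enter only the ITT analysis, which does not bear on the formal conclusion.

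PP is often preferred in non-inferiority trials because deviations tend to dilute a true difference. That argument does not apply when exclusion depends on outcome. If early failures are more frequent or more severe on CBL-102, leaving them out moves the estimated difference towards zero, in favour of non-inferiority. PP could then pass while ITT fails, and the written rule would still report non-inferiority. Any discussion of the conflict would take place after unmasking.

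The route is narrow. A failure first found at Visit 4 stays in PP. Only failures that surface earlier are lost: by self-report, at an unscheduled visit, or at an on-site Visit 3.

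**Working it through.** **Inputs from Protocol 7.3 and 7.4 (SAP 3.6 gives the same design figures):** one-sided α 2.5%, power 90%, margin 2, SD 2.5, 33 evaluable per arm, 10% dropout plus 10% violations, 84 randomised 1:1.

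**1. The plan's own figures reproduce.** With a true difference of 0 (not stated, but it returns the plan's N):

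- n per arm = 2 × [2.5 × (1.960 + 1.282) / 2]² = 32.84, rounded up to 33.
- 33 / (1 − 0.20) = 41.25, rounded up to 42 per arm, or 84 in total.
- With the t distribution, power at 33 per arm is 89.3%.

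The sample size is sound; the issue is the decision rule.

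**2. Sensitivity of the PP result.** SE = 2.5 × √(2/33) = 0.615. PP passes when the observed difference is below 2 − 1.998 × 0.615 = 0.77. Two or three subjects can matter on this scale.

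**3. False non-inferiority under PP alone.** Assume that an excess fraction f of the test arm leaves early and that these subjects are g points worse than completers. Then

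PP difference = all-randomised difference − f × g.

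Set the all-randomised difference at the margin, 2. The chance that PP passes follows from the noncentral t distribution with 64 degrees of freedom and noncentrality f × g / 0.615. For f = 10% and g = 4 this is 0.40 / 0.615 = 0.65, giving 9.3%. The values of f and g are assumptions; the documents give neither.

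| Excess early failures, test arm | g = 1 | g = 2 | g = 3 | g = 4 |
|---|---|---|---|---|
| none | 2.5% | 2.5% | 2.5% | 2.5% |
| 1 of 34 | 2.8% | 3.1% | 3.5% | 3.8% |
| 5% | 3.0% | 3.6% | 4.3% | 5.0% |
| 10% | 3.6% | 5.0% | 6.9% | 9.3% |

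The 10% row needs the whole projected dropout to be early, excess and outcome-related in the test arm, so it is an upper limit.

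**4. Requiring both sets.** Simulation used nested PP and ITT sets, unadjusted two-sample 95% intervals and at least 200,000 trials per scenario. With 33 PP subjects per arm, 2 of 35 or 3 of 36 test-arm subjects lost, and g from 1 to 4, PP alone gives about 3.1% to 7.7%. The both-sets rule gives about 2.0% to 2.3%. This assumes that every early leaver has a staining score.

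**5. Cost in power.** True difference 0, 33 PP subjects per arm, 2 to 9 further subjects per arm in ITT:

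| Added ITT subjects, both arms | Power, both sets required |
|---|---|
| like completers | about 88.2% to 88.6% |
| 3 points worse | about 87.2% to 87.6% |
| 4 points worse | about 85.9% to 87.0% |

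PP alone has 89.3%. With 36 PP subjects per arm and 4 added per arm, joint power is about 89.4% even at 4 points worse.

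**The case against.** The strongest reply is that this is a prespecified choice on which protocol and SAP agree, and that PP as the deciding set in a non-inferiority trial is recognised practice. The ITT analysis is mandatory and uses the same model, so a discordant result would be visible. SAP 7.3 already reports discontinuations and reasons by group. The investigator is masked, and major deviations are confirmed at masked review.

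The exposed group is also small. The 10% dropout has no stated time limit. If it were spread evenly to Day 90, about 42 × 0.10 × 28/90 = 1.3 subjects per arm would leave by Day 28 for any reason. One excess loss raises the error only to 2.8% to 3.8%. Subjects discontinued for over-use, as assessed at Visit 4, have reached Visit 4, so the completion rule does not remove them.

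The remedy is incomplete too. ITT needs at least one post-baseline assessment, and the termination assessments are worded as something that should happen. Protocol 7.6.1 also ties the endpoint to scheduled follow-up visits, which leaves some doubt whether a termination score counts.

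Most of this stands as a limit on size. It does not remove the gap. Visibility of the ITT result does not alter the formal conclusion. Masked review governs deviations, not the completion rule. Subjects are not described as masked, and early exits would mostly begin with their reports. On the termination score, Protocol 7.6.9 expressly applies last observation carried forward to early discontinuers, so it can be used; one sentence would settle it.

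**Conclusion.** The concern holds. The formal conclusion rests on PP alone, outcome-driven withdrawal before Day 28 removes a subject from that set without a deviation, and no rule covers disagreement between PP and ITT.

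The likely effect is modest: from 2.5% to between about 3% and 5% for one or two excess early failures on the test product, and 9.3% at the extreme examined. These figures rest on assumed excess and severity, an SD of 2.5, 33 PP subjects per arm, and no baseline adjustment. If early exits are equal in number and severity in both arms there is no bias, and nothing in the documents suggests that they will differ. The change is worth making because the gap is in the primary decision rule and closing it is cheap. It should be made, but the design does not fail without it.

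**What to change.** In the protocol synopsis, Protocol 7.6.1 and SAP 7.5:

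1. State that non-inferiority is concluded only if the upper 95% bound is below 2 in both the PP and the ITT analyses.
2. State that a subject who leaves before Visit 4 enters the ITT analysis with the staining score from the early-termination visit, under the existing carry-forward rule (Protocol 7.6.9, SAP 7.12).
3. Report by arm the number of early leavers with no post-baseline staining score, because ITT stays incomplete for them.

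No withdrawal or other clinical rule needs to change.

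**Cost.** One or two sentences in each place; both analyses are already planned. Power falls by about 1 point if the added subjects resemble completers, and by about 2 to 3.5 points if they are 3 to 4 points worse in both arms. N = 84 need not change. Restoring the power in full would take 36 PP subjects per arm, or 36/0.8 = 45 randomised per arm (90 in total), which is optional.

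The SAP already lists actual sites, so the study appears to be under way, and a protocol amendment needs ethics approval (Protocol 8.6). If that route is closed, the rule can be recorded in SAP sections 4 and 7.5 before the treatment codes are broken.
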